Study Duration	
The anticipated timeline for this study is as follows:
 
 • Subject enrolment begins: Sept 2016 • Last subject visit anticipated: Jan 2017 • Visits: 
V1: Screening & optimize prescription for Avaira toric V2: Dispense new or optimized prescription Avaira Toric - this visit may not be necessary if subjects habitually wear optimized power Avaira Toric V3: Baseline Avaira Toric & Avaira Vitality Toric dispense V4: 2 week follow-up wearing Avaira Vitality Toric V5: 1 month follow-up wearing Avaira Vitality Toric & Exit

Patient Population	Habitual toric contact lens wearers that provide written informed consent and meet protocol entry criteria.
Sample Size	Target enrollment of 48 subjects with the hope of at least 44 subjects being in the analysis cohort.
Study Center Location (US)	USA
Number of Centers	Multi-Center, 4 sites.

Patient Follow-up	
Patients enrolled in this study will be followed up after the each lens dispensing session. Follow-ups at:
 
 ○ at least 1 month lens wear of Avaira Toric ○ 2-week and 1 month wear of Avaira Vitality Toric
Primary Endpoints	
 • Visual acuity with contact lenses, • Lens fit performance (centration, rotation, blink movement) • Investigator's fit acceptability
[REDACTED]	[REDACTED]

Table of Contents

1	Introduction	8
2	Study Objective	8
3	Study Hypothesis	8
3.1	Study Hypothesis.....	8
4	Study Design	9
5	Study Population	9
5.1	Sample Size Calculation.....	9
6	Investigational Sites	9
6.1	Number of Sites.....	9
6.2	Investigator Recruitment.....	9
7	Ethics Review / Statement of Compliance	10
7.1	Relevant Standards / Guidelines	10
7.2	Institutional Review Board	10
7.3	Clinical Trial Registration	10
7.4	Informed Consent.....	10
8	Potential Risks and Benefits to Human Subjects	10
9	Materials and Methods	11
9.1	Subjects.....	11
	Inclusion criteria	11
9.2	Study Materials.....	13
9.2.1	Contact lens.....	13
9.2.2	Contact Lens care.....	13
9.2.3	Rewetting/ lubricating eye drops	13
9.2.4	Storage of Study Medications/Treatments	13
9.2.5	Clinical Supply Inventory.....	14
9.2.6	Disposal of Consumables	14
9.2.7	Masking and Control of Study Materials.....	14
9.2.8	Ordering and Accountability of Study Materials.....	14
9.3	Visit Schedule and Procedures.....	14
9.3.1	Visit 1: Screening visit & Establish Optimum Prescription	15
9.3.2	Visit 2: Dispense of Avaira Toric Lens.....	18

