9.3.3	Visit 3: Baseline with Avaira Toric & Dispense of Avaira Vitality Toric lenses.....	19
9.3.4	Visit 4: 2-week follow up for Avaira Vitality Toric	21
9.3.5	Visit 5: 1-month follow up on Avaira Vitality Toric Lenses & Study Exit	22

10	Adverse Events and their Reporting	24
10.1	Adverse Response Definitions	24
10.2	Procedures for Adverse Events	26
10.3	Reporting Adverse Events	27
10.4	Discontinuation from the Study	27
11	Statistical Analysis	27
11.1	Statistical analysis	27
12	Data Quality Assurance	28
12.1	Study monitoring	28
12.2	Record keeping	28
12.3	Record retention	28
12.4	Data Entry / Data Management	28
12.5	Confidentiality	29
12.6	Publication	29
13	Study Costs and Subject Compensation	29

1 Introduction

The utilization of soft toric contact lenses has increased significantly over the past few years. CooperVision (CV) produces a number of toric contact lens products including the Avaira toric brand (Enfilcon A) and Avaira Vitality brand (Fanfilcon A). All Enfilcon A toric lenses and Fanfilcon A toric lenses feature CooperVision's exclusive Aquaform® Technology and PEG (Polyethylene Glycol). This combination of material technologies provides a contact lens with high oxygen permeability that is naturally wettable and offers unique comfortable experience.

This study is designed to evaluate how adapted contact lens wearers of Enfilcon A toric lenses will perform following a refit with Fanfilcon A toric lenses, a novel soft contact lens with optimized lens geometry and enhanced water content and UV protection, over one month of daily wear. Overall lens wear experience, including visual quality, lens fit and subjective responses will be assessed.

2 Study Objective

The aim of this study is to determine if adapted contact lens wearers of Enfilcon A toric lenses can be confidently refit into Fanfilcon A toric lenses and be successful after at least one month of daily wear.

Primary outcomes:

- High contrast distance visual acuity (Snellen) with contact lenses
- Lens fit performance (centration, corneal coverage, post blink movement)
- Investigator's fit acceptability

3 Study Hypothesis

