3.1 Study Hypothesis

- Null hypothesis (Ho): There is no difference in lens performance between Enfilcon A toric and Fanfilcon A toric lenses for the key variables measured.
- Alternative hypothesis (H1): There is a difference in lens performance between Enfilcon A toric and Fanfilcon A toric lenses for the key variables measured.

4 Study Design

This is a prospective, multi-center, subject-masked, bilateral wear, two month dispensing study comparing the clinical performance of the Fanfilcon A toric lenses following a refit and adaptation with Enfilcon A toric lenses (Table 1). The subjects will be fit bilaterally into the Enfilcon A toric lenses at the first visit (or continue wearing their habitual Enfilcon A toric lenses) which will be worn for a minimum of one month and then subjects will be re-fit bilaterally with a pair of Fanfilcon A toric lenses for another month of daily wear. After the dispensing Fanfilcon A toric lens, subjects will return for follow up evaluations after 2 weeks, and 1 month.

The subjects will be advised that they may be dispensed with either Enfilcon A toric lenses OR Fanfilcon A toric lenses, however all subjects will be refit with Fanfilcon A toric lenses. The participant will not be informed on which study lens he/she is wearing during the second month but the investigator will have this information.

5 Study Population

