5.1 Sample Size Calculation

A sample size calculation was provided based on the 'subjective comfort just before lens removal' (0-10 scale) data on file at CooperVision from study EX-MKTG-63, which gave a standard deviation of 2.4. For an alpha level of 0.05 and power of 0.8, a sample size of 44 will detect a difference of 1.04, which has been confirmed as acceptable by the sponsor.

We recommend dispensing lenses to at least 48 subjects to be sure to have 44 subjects in the eligible analysis population ie. 12/13 at each of the 4 sites.

6 Investigational Sites

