In some circumstances a repeated Dispensing visit (Visit 2R) may need to be scheduled if an over-refraction was found and lenses in a different prescription need to be ordered. The maximum total number of repeat dispense visit permitted will be one (App 2R)

9.3.3 Visit 3: Baseline with Avaira Toric & Dispense of Avaira Vitality Toric lenses

- If subject is an habitual Avaira Toric wearer with optimum prescription then Visit 3 will be scheduled at least 29 days after **Visit 1**
- If subject was fit into new or modified Avaira Toric lenses then Visit 3 will be scheduled at least 29 days after **Visit 2**
- The subject should wear the lenses for a minimum of 2 hours prior to the appointment. If the subject attends without lenses or with less than 2 hours of lens wear on that day and they are not having any problems with their lenses, the visit should be rescheduled, if possible within the visit window. The following clinical test variables will be recorded on the CRFs as indicated:

Visit 3a: Baseline for Avaira Toric Lenses (App 7A)

- Confirm if any changes to health or medications
- [REDACTED]

[REDACTED]

[REDACTED]

[REDACTED]

[REDACTED]

[REDACTED]

- [REDACTED]
- Vision
 - High contrast distance monocular Snellen visual acuity
 - High contrast distance binocular Snellen visual acuity
- [REDACTED]
- Lens fit
 - Lens centration (centered/slightly decentered/substantially decentered)
 - Corneal coverage [Y/N]
 - [REDACTED]
 - Post-blink movement (0-4 Likert scale)
 - [REDACTED]
 - [REDACTED]
 - [REDACTED]
 - [REDACTED]
 - Overall fit acceptance (0 - 4) and reason if Grade 2 or less 1 step.
- Remove study lenses and perform slit lamp examination. A minimum 5 minute washout time after fluorescein insertion is required prior to lens insertion.

Visit 3b: Fitting and Dispensing of Avaira Vitality Toric Lens (App 7B)

The performance of the lenses should be assessed after 10-15 minutes settling time and the following variables will be assessed:

- Record the parameters of the lenses, lot number, and power, on the Dispensing CRF (App 7B).
- Vision
 - High contrast distance monocular Snellen visual acuity
 - High contrast distance binocular Snellen visual acuity
- [REDACTED]
- [REDACTED]
- [REDACTED]
- Lens fit
 - Lens centration (centered/slightly decentered/substantially decentered)
 - Corneal coverage [Y/N]
 - [REDACTED]

– Post-blink movement (0-4 Likert scale)

– [REDACTED]
[REDACTED]
[REDACTED]
[REDACTED]
[REDACTED]

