11.1 Statistical analysis

Descriptive statistics will be provided on information regarding baseline variables (e.g., age, gender). Differences between lenses and over time will be compared using Paired t-tests. Paired t-tests

/analysis of variance for normal (interval/continuous) data. The appropriate test will be selected based on tests of normality. Means and standard deviations will be provided for each variable.

A Binomial test will be used to analyze the results for the count data of subjective preferences. The number of "no preference" will be evenly distributed to the two options on the basis they would be equally likely to choose either. All subjects who were evaluated will be used in the analysis. In the event of missing data, individual data points will be excluded in the analysis and not extrapolated from the collected data.

12 Data Quality Assurance

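### Post-blink movement is compared only by its mean; if the 0-4 scale has its best grade inside the range, tight and loose fits offset each other and two-sided worsening goes largely undetected

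*Combined protocol and SAP*

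**What the plan says.** Movement appears in both lists of primary measures. The synopsis has "Lens fit performance (centration, rotation, blink movement" and section 2 has "Lens fit performance (centration, corneal coverage, post blink movement". The two lists differ in their other components, but movement is common to both.

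Section 9.3.3 records the item on both lenses at Visit 3 as "Post-blink movement (0-4 Likert scale", and the same item returns at Visit 5a. The readable text gives no anchors, no best grade and no acceptable range for it. Overall fit acceptance is graded separately, also 0-4, with a threshold for dispensing and a reason recorded for low grades.

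On analysis, section 11.1 states: "Differences between lenses and over time will be compared using Paired t-tests". It ties t-tests and analysis of variance to normal data and adds: "The appropriate test will be selected based on tests of normality". It names no alternative test for non-normal data. For summaries it states: "Means and standard deviations will be provided for each variable". The binomial test in that section is for preference counts only.

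The null hypothesis in section 3.1 is undirected: "There is no difference in lens performance between Enfilcon A toric and Fanfilcon A toric lenses for the key variables measured". Nothing there says which change in movement counts as worse.

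**The concern.** A mean works as a measure of quality when higher is better, or lower is better, throughout the scale. Amount of movement need not behave that way: a lens that hardly moves and one that moves too much can both fit poorly, with the best grade between them. On such a scale the mean has no fixed relation to quality. If the test lens were too tight in some eyes and too loose in others, the two groups would pull the mean in opposite directions and the paired difference could be near zero. If the mean did shift, the shift alone would not show whether fit had improved or worsened.

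The lenses differ in base curve (8.5 against 8.4) and diameter (14.5 against 14.2) according to Table 1, so some change in movement is plausible. At stake is whether the planned test of this primary component can be interpreted.

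**Working it through.** **The plan's own figure.** Section 5.1 uses a comfort score, "which gave a standard deviation of 2.4", with alpha 0.05, power 0.8 and a difference of 1.04. Taking 2.4 as the SD of paired differences and alpha as two-sided, the normal approximation is n = (1.960 + 0.842)² × 2.4² / 1.04² = 41.8. The exact paired t calculation gives n = 44 with power 0.802, so the stated 44 reproduces. It concerns comfort; no power is given for movement.

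**A worked example of the mechanism** (assumed optimum at grade 2). Control: all 44 subjects at grade 2. Test: 34 at grade 2, 5 at grade 0, 5 at grade 4.
- Raw grades: the mean difference is (5 × (−2) + 5 × 2)/44 = 0, so t = 0 and p = 1.
- Distance |grade − 2|: mean 20/44 = 0.4545; variance (40 − 44 × 0.4545²)/43 = 0.719; SE = √(0.719/44) = 0.128; t = 3.56, p = 0.0009.
- Exact McNemar, 10 against 0: p = 2 × 0.5¹⁰ = 0.00195.

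**Less extreme distributions** (all assumed). There is one grade per subject, n = 44, grades on the two lenses are independent, grade 2 is best, and grades 0 and 4 are extreme. The control lens has grades 0 to 4 at 2/13/70/13/2%, so 4% are extreme. The entries are the percentage of simulated trials with p < 0.05 (20,000 runs for the t-tests, 2,000 for Wilcoxon and McNemar).

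| Test-lens grades 0-4 (%) | Extreme | Test-lens mean | Raw t | Wilcoxon | Distance t | McNemar |
|---|---|---|---|---|---|---|
| 2/13/70/13/2 | 4% | 2.00 | 4.9 | 5.3 | 5.2 | 0.6 |
| 5/20/50/20/5 | 10% | 2.00 | 4.9 | 3.8 | 50 | 8 |
| 10/20/40/20/10 | 20% | 2.00 | 5.0 | 5.1 | 89 | 52 |
| 15/20/30/20/15 | 30% | 2.00 | 5.1 | 4.3 | 99 | 89 |
| 16/20/40/20/4 | 20% | 1.76 | 23 | 24 | 89 | 54 |
| 20/20/45/13/2 | 22% | 1.57 | 64 | 64.5 | 82 | 62 |

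**Hand check of the third row.** Both raw means are 2.00, so the raw test can reject only at alpha. Mean distance is 0.34 for control and 0.80 for test, a difference of 0.46. The distance variances are 0.42 − 0.34² = 0.304 and 1.20 − 0.80² = 0.560. The SE is √(0.864/44) = 0.140, and 0.46/0.140 = 3.28. Against a critical value of 2.02 this gives power of about 90%, in line with the simulated 89%.

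**What the table shows.** Under symmetric worsening the raw-mean test rejects no more often than when nothing has changed. A rank test chosen after a normality check does no better. When the worsening is mainly towards one end, the gap shrinks to 64% against 82%.

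**The case against.** The strongest reply is that the decisive premise cannot be seen. The readable text gives no anchors, and the forms that carry the item (App 7A, 7B and 12) are not in the text. A reader might infer that both ends of this scale are established as failures; the documents do not say so. The 0-4 scales whose direction can be inferred, such as fit acceptance, run one way, and if movement does too there is no cancellation. This stands as a condition on the whole point. Two features make an amount scale the more natural reading without proving it: movement is graded apart from the fit acceptance grade, and it is the only 0-4 item called a Likert scale.

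A reader might also infer that the CRF lacks anchors, or that rotation has the same fault. Neither is supported: the forms are unseen, and no recording format for rotation is readable.

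Three features limit the harm. Investigator's fit acceptability is itself a primary outcome and may register badly moving lenses. The fit check at Visit 3b removes some poor fits before Visit 5, although it acts on overall acceptance after 10-15 minutes' settling and subjects removed there drop out of the paired comparison. The reported SD would widen: in the third row of the table from √0.42 = 0.65 to √1.20 = 1.10. These make it less likely that a worse fit passes unnoticed. They do not give movement an interpretable test, because no planned test uses the spread.

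Finally, full cancellation needs nearly symmetric worsening, and the documents give no specific reason to expect it. That stands too, but partial cancellation is already costly: 23% against 89% at 16% tight and 4% loose.

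**Conclusion.** The point holds conditionally. It is certain from the text that movement is part of a primary outcome, that section 11.1 plans a mean, an SD and a paired t-test for it, and that no grade counts or acceptable-range analysis are specified. If the scale is two-ended, that analysis has little power against two-sided worsening: about 5% against about 89% for distance from the optimum when extreme grades rise symmetrically from 4% to 20% at n = 44. These figures rest on assumed distributions, an assumed optimum at grade 2 and independent grades on the two lenses. The loss is smaller when worsening is mostly one-sided, and nil on a one-way quality scale.

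It would be going too far to conclude that the trial would declare the lenses equal in fit when they are not, since fit acceptability and the reported SD offer other routes to seeing a problem. The supported conclusion is that one primary component may lack a test that can be interpreted, and that this can be put right cheaply.

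**What to change.** In section 11.1:
- Report the count of subjects at each movement grade for each lens, whatever the direction of the scale.
- State, by reference to the CRF's own anchors, whether the scale is two-ended and which grades are optimal and acceptable. Settle this before grades are compared by lens.
- If it is two-ended, make the inferential comparison on |grade − optimum|, paired, Visit 5 against Visit 3a. Support it with the paired proportion outside the acceptable grades by exact McNemar, and keep the raw mean as description only.
- State how the two eyes are combined. If they are averaged, take the distance in each eye first, so that a tight eye and a loose eye in one subject do not cancel.
- If the scale is one-way, say so; the grade counts are then the only addition under this point.

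The cost is some SAP wording, one derived variable and a little extra analysis, with no new data. McNemar should not carry the comparison alone: for a rise from 4% to 10% its power was about 8%, against about 50% for distance from the optimum.

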9.1 Subjects

Approximately 48 astigmatic subjects will be enrolled with the aim of at least 44 subjects successfully completing the study and being part of the analysis population. Subjects will either be adapted wearers of Avaira Toric lenses, or they will be refit for a minimum of one month lens wear before being refit to Avaira Vitality Toric. Each subject will be required to attend up to five scheduled study visits over a period of approximately two months.

Each subject will be given a unique ID number. All subjects who sign a consent document will be included in the subject enrollment log which will include; subject ID, date of consent, date of screening, date of study completion, date of discontinuation (if req'd), reason for discontinuation (if req'd). (App 20)

Additionally, all subjects must meet the study inclusion and exclusion criteria listed below.

Inclusion criteria

A person is eligible for inclusion in the study if he/she:

- Is between 18 and 40 years of age (inclusive)
- Has had a self-reported eye exam in the last two years
- Is a habitual soft toric lens wearer
- Can be successfully fit with study lenses (\geq grade 2 fit acceptance)
- Has a contact lens spherical prescription between -1.00 to -6.00D with a cylinder between -0.75 and -1.75D (inclusive)
- Has a spectacle cylinder of at least 0.75D in each eye.

- Can achieve best corrected spectacle refraction distance visual acuity of 20/25 (0.10 logMAR) or better in each eye.
- Can achieve a distance visual acuity of 20/30 (0.18 logMAR) or better in each eye with the study contact lenses.
- Has clear corneas and no active ocular disease
- Has read, understood and signed the information consent letter
- Has a contact lens refraction that fits within the available parameters of the study lenses
- Is willing to comply with the wear schedule (at least 5 days per week, > 8 hours/day assuming there are no contraindications for doing so)
- Is willing to comply with the visit schedule.

Exclusion Criteria

A person will be excluded from the study if he/she:

- Has a history of not achieving comfortable CL wear (5 days per week; > 8 hours/day)
- Presents with clinically significant anterior segment abnormalities
- Presents with ocular or systemic disease or need of medications which might interfere with contact lens wear
- Presents with slit lamp findings that would contraindicate contact lens wear such as:
 - Pathological dry eye or associated findings

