9.2 Study Materials

9.2.1 Contact lens

All subjects will have worn, or be fit with an optimized prescription in Avaira Toric for at least one month before being fit and dispensed the Avaira Vitality Toric. Details of the contact lenses are shown in Table 1.

The Avaira Vitality Toric lenses will be provided by the Sponsor. The sites may be asked to source the Avaira Toric lenses as needed and retain invoices for reimbursement.

Table1: Study lenses

Brand	Avaira Toric lenses (Control)	Avaira Vitality lenses (Test)
Manufacturer	CooperVision	CooperVision
Material	Enfilcon A	Fanfilcon A
Water Content	46%	55%
Base Curve	8.5	8.4
Lens Diameter	14.5	14.2
Lens Powers Sphere	-1.00 to - 6.00 (0.25 steps)	-1.00 to - 6.00 (0.25 steps)
Lens Power Cylinder	-0.75, -1.25, -1.75	-0.75, -1.25, -1.75
Axis	10 ^o to 180 ^o (10 ^o steps)	10 ^o to 180 ^o (10 ^o steps)
Replacement schedule	Daily wear	Daily wear

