9.3.1 Visit 1: Screening visit & Establish Optimum Prescription

This visit will be performed to assess eligibility and to establish optimum prescription. The subjects should attend the first visit wearing their habitual lenses and having worn them that day for at least 2

hours prior to the visit. If they are not wearing their lenses, please reschedule the visit. The following baseline measurements and assessments will be recorded:

- The subject will be required to read and sign an Informed Consent Form prior to enrolment (App 18). When the subject has signed the consent form, the subject will be considered to be enrolled on to the study.
- The person explaining the consent/ the Investigator should also sign the consent form.
- The subject will be provided with a copy of the consent and the original will be kept in the subject's paper chart. It may also be scanned into the subject's electronic medical record (EMR) file.
- The subject is assigned with a Subject ID number. Subjects must be enrolled sequentially.
- The subject enrollment log will be updated (App 20).
- Screening Form (App 1) will be completed to assess eligibility with respect to habitual lens wear, ocular and medical history.
- Subject's age and gender
- Details of current lens:
 - Brand
 - Power(s)
 - Replacement schedule
 - Lens age (days)
- Current lens care used
- Use of rewetting/lubricating drops
- Habitual lens wearing times:
 - Average daily wearing time (hours/day)
 - Average comfortable wearing time (hours/day)
 - Number of days/week (lenses are worn).
- Health history and medications
- Overall habitual lens fit acceptance (0 - 4) and reason if Grade 2 or less and lens orientation
- Habitual high contrast, distance monocular Snellen visual acuity
- Habitual high contrast, distance binocular Snellen visual acuity
- Over-refraction with habitual lenses and Snellen visual acuity with over-refraction
- Remove habitual lenses.
- Automated refraction including keratometry readings
- Subjective sphero-cylindrical refraction and high contrast monocular and binocular Snellen visual acuity
- Determine if subjects need to be scheduled for Visit 2 or Visit 3:
 - For a subject who is a current Avaira Toric wearer and does not require a change in prescription, please complete Avaira Vitality Prescription Form (App 3). Subject can be scheduled for Visit 3 when Avaira Vitality Lenses are available (≥ 29 days after screening visit 1).

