9.3.2 Visit 2: Dispense of Avaira Toric Lens

If this visit is required, it will be scheduled when the Avaira Toric lenses are available. This visit will be performed to fit and dispense new or modified power Avaira Toric lenses. Hence, this visit is only necessary if a change in Avaira Toric power is required or if a re-fit into Avaira Toric is required for adaptation. The following measurements and assessments will be recorded:

- Ensure no changes to health/medications and no contraindications for lens wear (App 6A)
- Complete biomicroscopy (App 4)
- A minimum 5 minute washout time after fluorescein insertion is required prior to lens insertion. The performance of the lenses should be assessed after 10-15 minutes settling time. The following variables will be assessed (App 6A)
- Record the parameters of the lenses, lot number, and power, on the Dispensing CRF
- Vision
 - High contrast distance monocular Snellen visual acuity
 - High contrast distance binocular Snellen visual acuity
- Over- refraction and Snellen visual acuity with over-refraction
 - Amendments to the distance sphere power, cylindrical power and/or axis can be made. Record the number of trial lenses required to achieve a successful fit

- Overall lens fit acceptance (0-4) and reason if Grade 2 or less and record lens orientation
- To be successfully dispensed, subjects must show \geq Grade 2 lens fit acceptance with the trial fit lens and must be correctable to 20/30 (0.18 logMAR) or better in each eye with the study contact lenses.
- If the lenses are not a suitable fit to be dispensed then the subject will be discontinued and an Exit Form (App 13) will be completed.
- If successful lens fit and no lens modification is needed, then complete Avaira Vitality Prescription Form (App 3)
- The subject will be instructed to wear the lenses on a daily wear basis, (at least 5 days/week, >8 hours/day), until Visit 3 appointment, unless they experience a problem which warrants lens removal.
- The Investigator or a clinical assistant will review instructions and warnings for lens wear and care, when to remove lenses, and other important issues with the subject.
- Subjects, who appear unable or unwilling to follow instructions to a degree that, in the Investigator's opinion, jeopardizes the subject's wellbeing or the validity of the study, will be discontinued. The reason for discontinuation will be documented.

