– Overall fit acceptance (0 - 4) and reason if Grade 2 or less.

- [REDACTED]
[REDACTED]
[REDACTED]
[REDACTED]
[REDACTED]
[REDACTED]

- To be successfully dispensed, subjects must show >Grade 2 lens fit acceptance with the trial fit lens and must be correctable to 20/30 (0.18 logMAR) or better in each eye with the study contact lenses.
- If the lenses are not a suitable fit to be dispensed then the subject will be discontinued and an Exit Form (App 13) will be completed.
- The subject will be instructed to wear the lenses on a daily wear basis, (at least 5 days/week, >8 hours/day), until Visit 4 appointment, unless they experience a problem which warrants lens removal.
- The Investigator or a clinical assistant will review instructions and warnings for lens wear and care, when to remove lenses, and other important issues with the subject.
- Subjects, who appear unable or unwilling to follow instructions to a degree that, in the Investigator's opinion, jeopardizes the subject's wellbeing or the validity of the study, will be discontinued. The reason for discontinuation will be documented.
- The subject will be discharged and asked to return for a follow-up visit (V4) after 2-weeks

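### Visit 3b dispenses the test lens only above grade 2 fit acceptance, while section 9.1 and Visit 2 accept grade 2 itself; probably a slip, with a one-character fix

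*Combined protocol and SAP*

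**What the plan says.** Three places in the combined protocol and SAP set a fit-acceptance threshold.

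- **Section 9.1, inclusion criteria:** "Can be successfully fit with study lenses (\geq grade 2 fit acceptance". The table headed "Table1: Study lenses" in section 9.2.1 lists both the control and the test lens.
- **Section 9.3.2, Visit 2 (control lens):** "subjects must show \geq Grade 2 lens fit acceptance with the trial fit lens".
- **Section 9.3.3, Visit 3b (test lens):** "To be successfully dispensed, subjects must show >Grade 2 lens fit acceptance with the trial fit lens".

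In the first two, the sign is greater-than-or-equal. In the third it is a plain greater-than.

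In both visit sections the next bullet gives the consequence without naming a grade: "If the lenses are not a suitable fit to be dispensed then the subject will be discontinued". Visit 3b also records "Overall fit acceptance (0 - 4) and reason if Grade 2 or less".

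Not everyone attends Visit 2. Apart from refits into the control lens, "this visit is only necessary if a change in Avaira Toric power is required". For a current control-lens wearer with no prescription change, section 9.3.1 says "Subject can be scheduled for Visit 3 when Avaira Vitality Lenses are available".

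**The concern.** The threshold decides who wears the test lens. In the visible text, Visit 3b is the first time the test lens is graded on the eye, so this bullet is the working rule for it. Taken with the discontinuation bullet, a subject graded exactly 2 meets section 9.1 but exits before any follow-up in the test lens. The control lens has no such gate: Visit 2 accepts grade 2, and subjects who skip Visit 2 face only section 9.1.

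Section 2 makes investigator's fit acceptability a primary outcome and sets the aim as success after a month in the test lens. A stricter gate on the test lens alone would filter out marginal fits before the 2-week and 1-month readings, which could favour that lens. Four sites holding two conflicting statements could also apply them differently.

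**Working it through.** **1. The sentences compared.** The Visit 2 and Visit 3b bullets match word for word, including the 20/30 acuity condition, except for the sign. Section 9.1 covers study lenses without separating control from test. The visible text gives no reason for a stricter test-lens gate; nothing is inferred from the redacted lines nearby. The prompt to give a reason at grade 2 or less does not support a strict rule, because Visit 2 has the same prompt beside its at-least-grade-2 rule. Visit 3a describes the scale as moving in steps of 1. If Visit 3b does the same, the literal rule admits grades 3 and 4 only.

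**2. Could the sign have been misread from the PDF?** The greater-than-or-equal sign survives 10 times in the extracted text: once each in section 9.1, section 9.3.1 and section 9.3.2, and 7 times in the adverse event table of section 10.1. Apart from Visit 3b, a plain greater-than sign appears 7 times: five for the 8 hours/day wear time, one for 0.75 mm of neovascularization and one for lens discontinuation of more than 1 day. None of those seven conflicts with another statement of the same rule. The Visit 3b sign does.

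**3. Which comparison is affected.** Visit 3b grades are recorded before the dispensing decision, and section 11.1 analyses all evaluated subjects. The Visit 3a versus Visit 3b comparison is therefore untouched. Only the 2-week and 1-month data can be.

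**4. Effect of one removed subject.** Assume that the subject would have stayed at grade 2 at 1 month, had control grade g at Visit 3a, and that the other n − 1 subjects have mean difference 0 (1-month test minus Visit 3a control).

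- Mean with the subject: ((n − 1) × 0 + (2 − g))/n = (2 − g)/n
- Mean without the subject: 0
- Shift on removal: (g − 2)/n

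| g | n = 48 | n = 44 |
|---|---|---|
| 0 | −2/48 = −0.042 | −2/44 = −0.045 |
| 1 | −1/48 = −0.021 | −1/44 = −0.023 |
| 2 | 0 | 0 |
| 3 | 1/48 = 0.021 | 1/44 = 0.023 |
| 4 | 2/48 = 0.042 | 2/44 = 0.045 |

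A positive shift favours the test lens. If the fit would have improved by 1 month, a positive shift would be smaller.

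**5. Retention.** The plan's own figure reproduces. A two-sided paired t-test at alpha 0.05, with 2.4 taken as the SD of the paired difference and a difference of 1.04, needs n = 44 (power 0.802). That calculation is for comfort, not fit. The loss allowance is 48 − 44 = 4 subjects (4/48 = 8.3%). This rule alone would exceed it only if 5 or more of 48 (5/48 = 10.4%) were graded exactly 2 at Visit 3b. With 43 left, the comfort power would be 0.793. This holds only if 48 counts subjects reaching Visit 3b. If 48 counts subjects dispensed the test lens, these exits do not draw on the allowance.

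**The case against.** The strongest reply is that the point rests on one character in machine-read text. An underlined greater-than sign could have lost its underline, and the otherwise identical sentence is what one would then expect. The surviving greater-than-or-equal signs do not show how an underlined sign would be read. The seven other plain signs are weak evidence too: five are one wear-time rule and the other two have no second statement to conflict with. This stands, and it is why the source must be checked first.

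Second, section 9.1 is an entry criterion, with the eligibility checklist completed at Visit 1. A later dispensing gate may be stricter without logical contradiction. This stands only in part: section 9.1 speaks of study lenses, Table 1 includes the test lens, and no reason for a stricter gate is visible.

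Third, the direction of bias is not certain. No dispensing gate applies to the Visit 3a reading, so a control grade of 0 or 1 is possible, and removal would then count against the test lens. That is correct, and the table includes those cases. They look less likely after a control fit accepted at grade 2 or better, but the documents cannot settle it.

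Fourth, no stated figure, test or sample size changes. That is also correct, and it supports a minor rating.

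**Conclusion.** The inconsistency holds as the text reads. Visit 3b is stricter for the test lens than section 9.1, and stricter than Visit 2 is for the control lens. It is probably a slip; no deliberate rule is claimed. The severity is minor, with medium confidence because the printed sign could not be checked.

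The total effect cannot be determined without the number of grade-2 fits at Visit 3b. Each removed subject shifts the 1-month mean difference by no more than 0.045 in either direction at n = 44, under the assumptions in step 4. If sites followed section 9.1, or if the source shows greater-than-or-equal, there is no effect.

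**What to change.** Check the sign in the source document. If it is a plain greater-than sign, change Visit 3b to grade 2 or more, to agree with sections 9.1 and 9.3.2. If a stricter rule was in fact intended, state the reason and align section 9.1.

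Report how many subjects, if any, were exited at exactly grade 2 in the test lens. Visit 3b already records the grade and the reason, and the Study Exit Form records the details of a discontinuation, so no new data are needed.

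The cost is one character in section 9.3.3, or nothing if an underline was lost in reading the PDF. There are no extra visits or subjects, and the targets of 48 and 44 stay. App 7B is not among the documents, so whether that form needs the same correction could not be checked.
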